### Sample Size / Minimum Detectable Effect Size Calculations

Table 4: Minimum Detectable Effect Size Calculations

|  |               |           |
|--|---------------|-----------|
| MDES (Proportion of a Standard Deviation)  |               | 0.24      |
| Proportion of Variance in Outcome Explained by Covariates  (R  ) | Child         | 0.5       |
|  | Family        | NA        |
|  | Social Worker | NA        |
| Intraclass Correlations Coefficient (ICCs)   | Family        | NA        |
|  | Social Worker | NA        |
|  | Team          | NA        |
| Alpha  |               | 0.05      |
| Power  |               | 0.8       |
| One-Sided or Two-Sided?    |               | Two-sided |
| Level of Intervention Clustering   |               | NA        |
| Average Cluster Size (if Cluster-Randomised)   |               | NA        |
| Sample Size  | Intervention  | 145       |
|  | Control       | 135       |
|  | Total         | 280       |

 This includes, and will most likely be most influenced by, a baseline measure of the outcome.

 By default we would recommend two-sided tests.

The sample size is determined through the resources available to deliver the intervention. Consequently, we have calculated the MDES based on the expected achieved sample sizes, a stratified random allocation design at the level of the UASC and the availability of a baseline measure, which assumes a pre-post correlation of 0.71, (i.e.  $R^2 = 0.5$ ). The PowerUp tool was used to calculate the sample size, using the BIRA2\_1f spreadsheet with 6 strata (4 local and 1 virtual Local Authority for low risk cases and one stratum for high risk cases) and an average block size of 47 to be allocated evenly to treatment and control groups.

It is assumed that 88% of the 280 cases will be moderate risk, i.e. 247 cases. These will be allocated 50: 50 to treatment and control, i.e. 123.5 cases per trial arm. Of the 12% assumed to be high risk (n = 33), it is assumed that 66% will be allocated to treatment (n = 22) and 34% to control (n = 11). Overall, 145 cases will be allocated to the treatment group and 135 to the control group, i.e. 52% of total cases will be in the treatment group.

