The MDES is a standardised effect size, i.e. it is measured in standard deviation units. This is advantageous when dealing with power analysis when outcome measure summary statistics such as the mean and standard deviation are unknown. We are not aware of reliable studies showing the distribution of the YP-Core among the population of interest studied here. However, to give an example of the MDES, a recent study by O'Reilly et al (2016) showed a mean score of 18.3, with a standard deviation of 7.6 among a sample of children aged 12-16 engaging for the first time with an intervention. Using these scores for illustrative purposes only, an MDES of 0.24 multiplied by the SD of 7.6 gives a score of 1.8. Given a control group mean of 18.3, we would require the intervention to produce a YP-Core mean score of 20.1, or above, in the treatment group to be detected using our design.

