## Analysis Plan

### Primary Analysis:

The primary and secondary impact analysis will use regression models to establish impact. For the primary outcome, the YP-CORE summary score will be the outcome variable. A binary indicator identifying whether the UASC was allocated to treatment (scored as unity) or control (scored as zero) will be included as a main effect in the model. The coefficient for this variable will carry the impact effect as the average difference in the YP-CORE outcome between the treatment and control group. The coefficient will be significance tested with a two-tailed alpha of  $P < 0.05$ , to establish the significance of the impact effect. Additionally, further variables will also be included in the regression, including the baseline measure of YP-CORE and an identifier for the stratification group. A single level OLS regression model with an identity link and Gaussian error term, will be used, given the lack of clustering in the data and the continuous nature of the YP-CORE outcome score.

$$\hat{Y} = a + bD + \sum_j^J z_j X_j + e \quad (1)$$

Where  $\hat{Y}$  is the predicted outcome score,  $a$  is the intercept,  $b$  is the coefficient carrying the impact effect,  $D$  is the binary indicator equalling unity for the treatment group and zero for the control group, and  $z_j$  represents coefficients for the baseline measure and the 5 stratum group indicator variables, with  $X_j$  representing the baseline score and the binary indicator variables for the 5 stratum indicator variables, and  $e$  is assumed to be normally distributed.  $J$  runs from 1 to 6, with 1 representing the mean centred baseline score and 2-6 the 5 stratum indicator variables. The excluded 6th stratum will be represented in the intercept.

Residuals from the regression model will be checked for heterogeneity and adjusted using a Huber-White approach, if required. Checks for heterogeneity will include a visual inspect of the plot of the residuals against the fitted values and Leven tests.

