There is the potential to increase the statistical power of the analysis further by including other predictor variables in the regression model. However, calculation of the standardised effect size will use the conditional total variance of the impact effect in its calculation. Using a minimum specification for the model means that the standardised effect size will only be conditioned on the baseline measure and the design variables. Consequently, the effect size

can be used in a meta-analysis study without concerns over comparability caused from effect sizes adjusting for different variables across different studies.

The impact estimator will be calculated using an intention to treat (ITT) analysis to maintain the integrity of randomisation in the allocation stage. This is the fundamental test of the success of the impact effect for this study. This ITT average treatment effect (ATE), however, is based on an ‘offer to treat’. In some circumstances, especially voluntary schemes, it is possible that some people offered the treatment do not participate in the treatment (non-compliers). In such cases, the ITT effect is diminished by those who have not participated. We can calculate the size of the impact effect on those who have participated using formula (2) below, which will be greater than or equal to the ITT average effect. It is also possible that some people in the control group actually receive treatment. This cross over is likely to happen in this particular study because of the over-ride option for young people in the high-risk stratum. In this case, the control group is contaminated by treatment, lowering the ITT estimate of the average treatment effect. Formula (3) below shows how we will adjust for this circumstance of dual cross overs, where the local average treatment effect is calculated as a weighted average of treatment compliers across the treatment and control groups.

in order to adjust for the presence of non-compliers in the treatment group, and assuming we can collect outcome scores for these people, we will also calculate the treatment on the treated, following equation 8 in Bloom (2006), as:

$$TT = \frac{\bar{Y}_t - \bar{Y}_c}{\bar{D}|Z=1} \quad (2)$$

Where the denominator is the proportion receiving treatment in the treatment group

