There is also the potential for cross-overs from the control group to the treatment group arising from the enforcement of the over-ride option from the BRC. Consequently, we may have cases who were allocated to treatment and either received treatment as intended or, through non-compliance, did not. Similarly, we may have people allocated to the control who, as intended, received no treatment, but also those with through the override option, received treatment. In such a situation, we will also include an estimate of the Local Average Treatment Effect (LATE), also described by Bloom (2006; equation 11):

$$LATE = \frac{\bar{Y}_t - \bar{Y}_c}{(\bar{D}|Z=1) - (\bar{D}|Z=0)} \quad (3)$$

Where the denominator is the difference in treatment rate between the treatment and control group.

These three impact effect estimators offer different perspectives on the success of the intervention. In practice, the LATE probably comes closest to capturing the impact which might be expected in a roll-out, given that the control group is likely to include a potentially influential minority of high-risk young people receiving treatment who consequently increase the baseline measure of no impact in the ITT estimator.

We note that this approach assumes the average impact effect for moderate risk cases is equal to the average impact effect for high risk cases, given that we anticipate cross-over from control groups only through the over-ride option in the high risk group. There is also the possibility that all cases in the high risk strata are overridden. If the over-ride option is exercised, we will test for the influence of the high-risk strata through sensitivity testing our results, as described below.

In addition to the estimators described above, we will provide a standardised impact effect (Glass’  $\Delta$ ). With only one primary outcome, there is no need to adjust for multiple significance testing, in line with WWCS recommendations.

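### The MDES of 0.24 is a valid ITT difference between arms, but the protocol presents it as the effect My View must produce and makes no allowance for the control crossover it expects

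*Protocol*

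**What the plan says.** The protocol's section Sample Size / Minimum Detectable Effect Size Calculations derives the MDES from the total of 280, R² = 0.5, two-sided alpha 0.05, power 0.8 and six strata. It expects 145 young people in the intervention arm and 135 controls, so that 52% are allocated to My View. On the covariate it "assumes a pre-post correlation of 0.71". There is no term for crossover or non-uptake. The section then gives an illustration, "an MDES of 0.24 multiplied by the SD of 7.6 gives a score of 1.8", and concludes that "we would require the intervention to produce a YP-Core mean score of 20.1, or above, in the treatment group to be detected using our design".

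The Primary Analysis section makes ITT the fundamental test. It says of people who are offered treatment but do not take part: "In such cases, the ITT effect is diminished by those who have not participated". Of treated controls it says: "This cross over is likely to happen in this particular study because of the over-ride option for young people in the high-risk stratum", and adds that this lowers the ITT estimate. It goes further: "There is also the possibility that all cases in the high risk strata are overridden". It adds treatment-on-the-treated and LATE estimators, and the Sensitivity Analysis section plans a re-run without high-risk cases if all of them are moved to treatment. None of this is carried back into the MDES.

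**The concern.** An MDES for an ITT analysis is a difference between arms as allocated. It equals the effect of the treatment itself only when the contrast in treatment received is complete. The illustration speaks of what the intervention must produce, so a reader will take the trial to have 80% power for a My View effect of 0.24 SD. The same protocol expects some controls to be treated, which shrinks the ITT difference below that effect.

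The sample size is set by delivery resources, so the MDES is the protocol's main statement of what a null result can rule out. If it is read as the effect of receiving My View, a null result could be taken to exclude an effect that the design had less than 80% power to find.

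**Working it through.** **Inputs** (Sample Size section unless stated): 247 moderate-risk cases at 1:1; 33 high-risk cases at 22:11; R² = 0.5; alpha 0.05 two-sided; power 0.8. The model is OLS on treatment, baseline and stratum indicators (Primary Analysis). Equal effects in moderate- and high-risk cases are the protocol's stated assumption. No attrition is assumed here.

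**Step 1: reproduce 0.24.** For a stratum-adjusted coefficient, the information is the sum over strata of n·p·(1−p).
- Moderate risk: 247 × 0.25 = 61.75
- High risk: 33 × (2/3) × (1/3) = 7.33
- Total: 69.08
- SE = √(0.5/69.08) = 0.0851
- MDES = (t₀.₉₇₅ + t₀.₈₀) × SE with 272 df, about 2.812 × 0.0851 = 0.239

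The unstratified form with 145 and 135 gives 0.238. Both round to 0.24. Power at 0.24 with full contrast is 80%.

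**Step 2: dilution.** If k of the 11 high-risk controls are treated, the contrast that the planned model sees is

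contrast = [61.75 + 7.33 × (1 − k/11)] / 69.08

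The ITT difference is 0.24 × contrast, with power from the noncentral t. The My View effect needed for 80% ITT power is 0.239 / contrast.

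| High-risk controls overridden | Contrast | ITT difference | Power for a My View effect of 0.24 | Effect needed for 80% |
|---|---|---|---|---|
| none | 1.000 | 0.240 | 80% | 0.24 |
| 2 of 11 | 0.981 | 0.235 | 79% | 0.24 |
| half | 0.947 | 0.227 | 76% | 0.25 |
| all 11 | 0.894 | 0.215 | 71% | 0.27 |

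A 20,000-run simulation of the planned OLS model gave 80.2% with no override and 70.9% with all 11 overridden. On the illustrative SD, 0.268 × 7.6 = 2.0 points, against the stated 1.8. The Randomisation section gives a high-risk allocation of 0.64 instead of 66:34; using 0.64 leaves the full-override power at about 71%.

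**Step 3: the planned re-run without high-risk cases.** SE = √(0.5/61.75) = 0.0900. With n = 247 and 240 df, the MDES is 0.253 and power at 0.24 is about 76%.

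**Step 4: direction of the illustration.** YP-CORE measures distress, so a lower score is better. A benefit of 1.8 points from a control mean of 18.3 gives 18.3 − 1.8 = 16.5 or below. The stated figure of 20.1 is 18.3 + 1.8, which is a worsening.

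**The case against.** The strongest reply is that nothing has been miscalculated. The primary comparison is between arms, the ITT effect is openly described as the effect of an offer, and 0.24 is the right MDES for it. That stands: a reader might infer that Table 4 is wrong, and it is not. The fault lies in how the illustration describes the figure.

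A second reply is that the protocol already discloses dilution and provides for it with treatment-on-the-treated, LATE, a count of overrides and the re-run without high-risk cases. The disclosure is real. But dividing by the contrast scales the estimate and its standard error together, so it restores no power, and the re-run is itself below 80% at 0.24.

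A third reply is that the loss is small. From override alone it is. Taking R² = 0.4 in place of 0.5 would by itself raise the MDES to about 0.26.

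Stronger readings are tempting but unsupported:
- A reader might take 71% as the expected power. The protocol calls crossover likely, but calls override of every high-risk case only a possibility, and it gives no rate.
- A reader might dilute by 124/135 = 0.919, which gives about 74%. That is not the planned model, which adjusts for stratum.
- A reader might add non-uptake and obtain much lower power. Non-uptake, and controls attending drop-in groups (Table 7), would lower power further, but the protocol gives no rate for either.

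Finally, the calculation depends on 33 randomised high-risk cases, and the protocol is inconsistent about them. The Summary counts about 33 young people for crisis intervention. The Activities section says that crisis clients, classified as high risk, cannot be randomised. The procedures list and the ethics section also exclude crisis cases. Table 3, Randomisation and Sample Size all randomise a high-risk stratum. This objection stands in full.

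**Conclusion.** The point holds as a mislabelled sensitivity statement, not as an arithmetic error. The design has 80% power for an ITT difference of 0.24. For an effect of receiving My View of 0.24, power is about 79%, 76% or 71% as 2, half or all of the 11 high-risk controls are overridden. The chance of missing such an effect therefore rises from about 20% to at most 29% from this source. The effect needed for 80% power is about 0.25 SD with half overridden and 0.27 SD with all overridden.

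These figures rest on the protocol's allocation numbers, R² = 0.5, equal effects across risk groups, full uptake and no attrition. If the 33 high-risk cases are not randomised, this source of dilution disappears and the n = 247 figures apply instead: MDES about 0.25, and about 76% power at 0.24.

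**What to change.** In the Sample Size section:
- Label 0.24 as the minimum detectable ITT difference between arms as allocated.
- State that the corresponding effect of receiving My View is about 0.25 SD if half of the high-risk controls are overridden and about 0.27 SD (2.0 points on the illustrative SD of 7.6) if all are. Add that it is larger with any non-uptake, for which the protocol gives no rate.
- State the MDES of the planned re-run without high-risk cases (n = 247) as about 0.25, with about 76% power at 0.24.
- Reword the illustration in terms of the ITT difference and correct its direction to about 16.5 or below.

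Reconcile the Summary, the procedures list, Activities and the ethics section with Table 3, Randomisation and Sample Size on whether high-risk and crisis cases are randomised, then keep whichever set of figures applies.

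The cost is some rewording and a few extra numbers, with a slightly less favourable stated sensitivity. Recruitment and data collection do not change.

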## Outcome Measures

### Primary outcome measure

The primary outcome measurement is the Young Person's Clinical Outcomes in Routine Evaluation (YP-CORE) measure. The YP-CORE is a measure of psychological distress and is widely used in mental health and school counselling services. It is freely available to use.

The baseline YP-CORE measurement will take place at the pre-assessment session for young people randomised i.e. both the treatment and control groups. Data will then be collected at the following timepoints:

- Treatment group:
  - Baseline at the pre-assessment session
  - After six My View sessions (midpoint)
  - After three months of My View (endline / post-treatment)
- Waitlist control group:
  - Baseline at the pre-assessment session
  - After three months of being on the waitlist (endline) – this will be at a second pre-assessment session before the young person starts My View
  - After six My View sessions (standard practice, not included in the evaluation)
  - After three months of My View (standard practice, not included in the evaluation).

---

 We have used 47 cases per block as an approximation to the 280 total required (i.e.  $47 \times 6 = 282$ ).

 <https://www.ncbi.nlm.nih.gov/pmc/articles/PMC6860299/>

 <https://www.corc.uk.net/outcome-experience-measures/core-measurement-tools/>

 If, for any reason, the midpoint questionnaire (after 6 sessions) gets delayed and therefore becomes close to the endline questionnaire (to be completed after three months), therapists may decide to only collect the endline.

The measure is brief, with just 10 items covering anxiety, depression, trauma, physical problems, functioning and risk to self. As such, this covers the following short-term outcomes included in the programme's theory of change:

- Psychological and emotional well-being
- Emotional self-regulation
- Safety and risk of harm

For each item, the respondent selects one response to indicate how they have been feeling over the last week:

- Not at all
- Only occasionally
- Sometimes
- Often
- Most or all of the time

Each of these responses has a score between 0 and 4 (some are reverse scored), meaning each question has a score between 0 and 4. The clinical score is calculated by multiplying the total mean score (total of all item scores divided by number of items completed) by 10. However, because the YP-CORE has 10 items, this calculation is identical to simply adding the raw score of all 10 items, providing all 10 items have been completed. This gives a simpler and quicker way for practitioners to arrive at the clinical score. The clinical score is the total out of 40.

Figure 6: YP-CORE scale

### OVER THE LAST WEEK.....

|   | Not at all                 | Only occasionally          | Sometimes                  | Often                      | Most or all of the time    |
|---|----------------------------|----------------------------|----------------------------|----------------------------|----------------------------|
| 1. I've felt edgy or nervous                        |  0 |  1 |  2 |  3 |  4 |
| 2. I haven't felt like talking to anyone            |  0 |  1 |  2 |  3 |  4 |
| 3. I've felt able to cope when things go wrong      |  4 |  3 |  2 |  1 |  0 |
| 4. I've thought of hurting myself                   |  0 |  1 |  2 |  3 |  4 |
| 5. There's been someone I felt able to ask for help |  4 |  3 |  2 |  1 |  0 |
| 6. My thoughts and feelings distressed me           |  0 |  1 |  2 |  3 |  4 |
| 7. My problems have felt too much for me            |  0 |  1 |  2 |  3 |  4 |
| 8. It's been hard to go to sleep or stay asleep     |  0 |  1 |  2 |  3 |  4 |
| 9. I've felt unhappy                                |  0 |  1 |  2 |  3 |  4 |
| 10. I've done all the things I wanted to            |  4 |  3 |  2 |  1 |  0 |

The administration of the YP-CORE measure should be done consistently so that potential deleterious effects of changes in administration are minimised. It will be collected by the therapist using translated versions to ensure consistency. The British Refugee Council already collects the YP-CORE meaning this outcome measure is already embedded in practice for the one-to-one therapy. However, we are aware that a different measure is used for group sessions – this will need to be adapted to ensure consistent outcome measurement across participants.

 Where there are missing data, the clinical score is calculated by multiplying the total mean score by 10. Re-scaling the clinical score is not recommended if more than one item is missing.

## Secondary outcome measures

The secondary outcome measurement is the short version of the Warwick–Edinburgh Mental Wellbeing Scale (SWEMWBS). The SWEMWBS is a measure of mental wellbeing and therefore provides a secondary measure of the programme’s short-term outcome relating to improving the mental and emotional wellbeing of young people.

The SWEMWBS has been validated for populations of young people aged 15 -21 (McKay & Andretta, 2017; Ringdal et al., 2018). It uses seven of the WEMWBS’s 14 statements about thoughts and feelings, which are positively worded. Similar to the YP-CORE, each statement asks how the young person has been feeling over the last two weeks (instead of one) and has five similar response options:

- None of the time
- Rarely
- Some of the time
- Often
- All of the time

The SWEMWBS is free to use following completion of a registration form^12.

The SWEMWBS will be collected at the same timepoints as the YP-CORE. Young people will complete the SWEMWBS with the support of an interpreter where needed and this will be collected by therapists. The SWEMWBS has also been translated into a number of languages and some of these have been validated both psychometrically and qualitatively.

To score the SWEMWBS, each statement has a score between 1 and 5 and all seven scores are summed. Scores range from 7 to 35 and higher scores indicate higher positive mental wellbeing. The total raw scores need to be transformed into metric scores using the SWEMWBS conversion table.

---

 <https://www.corc.uk.net/outcome-experience-measures/short-warwick-edinburgh-mental-wellbeing-scale-swemws/>

 <https://warwick.ac.uk/fac/sci/med/research/platform/wemwbs/using/non-commercial-licence-registration/>

 <https://warwick.ac.uk/fac/sci/med/research/platform/wemwbs/using/translations/>

[https://warwick.ac.uk/fac/sci/med/research/platform/wemwbs/using/howto/swemwbs\\_raw\\_score\\_to\\_metric\\_score\\_conversion\\_table.pdf](https://warwick.ac.uk/fac/sci/med/research/platform/wemwbs/using/howto/swemwbs_raw_score_to_metric_score_conversion_table.pdf)

Figure 7: SWEMWBS scale

| STATEMENTS   | None of the time | Rarely | Some of the time | Often | All of the time |
|--|------------------|--------|------------------|-------|-----------------|
| I've been feeling optimistic about the future      | 1                | 2      | 3                | 4     | 5               |
| I've been feeling useful                           | 1                | 2      | 3                | 4     | 5               |
| I've been feeling relaxed                          | 1                | 2      | 3                | 4     | 5               |
| I've been dealing with problems well               | 1                | 2      | 3                | 4     | 5               |
| I've been thinking clearly                         | 1                | 2      | 3                | 4     | 5               |
| I've been feeling close to other people            | 1                | 2      | 3                | 4     | 5               |
| I've been able to make up my own mind about things | 1                | 2      | 3                | 4     | 5               |

